11. STUDY EVALUATION AND TREATMENT PROCEDURES

11.1. Demographics

A self-reported demographic questionnaire will be administered at baseline to assess subject characteristics that include age, race/ethnicity, psychological health status, and health insurance status.

11.2. Medical History and Concomitant Medication

Subject medical conditions and medication usage will be reviewed, assessed, and documented at each study visit.

11.3. Measurement of Weight, Body Circumference and Calculation of Body Mass Index (BMI)

When the subject is weighed, s/he should be wearing only undergarments and an exam gown.

The weight will be measured in duplicate at each visit. If the two readings are discrepant, it should be repeated until two consecutive identical readings are obtained.

Height will be measured and recorded at the screening visit.

The BMI is calculated to one decimal place, using the subject's weight at each visit and the height value obtained at baseline. A BMI calculator is provided in Appendix D.

Body circumference measures will be performed with the subject standing feet together. The following circumference measurements will be made:

- Hip: measured at the widest part of the hips
- Waist: measured midway between the lowest rib and the iliac crest
- Chest: measured at the 4th intercostal space in the mid-clavicular line
- Neck: measured at the widest part of the neck

11.4. Biochemical Measurements

Fasting blood samples will be obtained at the screening and baseline visits, and at the 6- and 12-month follow-up visits. The following analyses will be performed:

- CBC (Complete blood count), including differential (screen and baseline visits only)
- Chemistry Panel 20 (screen and baseline visits only)
- Lipid levels and lipoproteins (triglycerides, LDL-C, HDL-C, and total cholesterol)
- Glucose, insulin, HbA1c
- High sensitivity C-reactive protein

11.5. Satiety Assessment

Visual analogue scales by Control of Eating Questionnaire (Appendix H) will be used to assess the subject's hunger, fullness, cravings and related dimensions of appetite.³³ The Eating Inventory (Appendix I) will be used to assess cognitive restraint, disinhibition, and hunger. These instruments will be administered at the baseline, 1 week, and 1, 6, 12 month(s) visits.

11.6. Patient Health Questionnaire 9 (PHQ-9)

The Patient Health Questionnaire 9 (PHQ-9) is to be used to assess the subject's level of depression prior to participation in the study. If the subject's score is ≥ 10 , s/he will not be enrolled into the study.

A sample of the PHQ-9 is provided in Appendix E.

11.7. Impact of Weight on Quality of Life (IWQOL– Lite)³⁴

The IWQOL-Lite is a subject-completed 31-item instrument that reliably measures how a subject's weight affects his/her quality of life in the five domains of physical function, self-esteem, sexual life, public distress, and work. The IWQOL–Lite will be collected at baseline and at the 6- and 12-month follow-up visits.

A sample of the IWQOL-Lite is provided in Appendix F.

11.8. Test for Helicobacter Pylori

A negative stool antigen test for *H. pylori* is required for study inclusion. The subject should be off antibiotics, antacids, and bismuth for 2 weeks, and not be bleeding before the testing. If the test reveals the subject is positive for *H. pylori*, the subject will be treated accordingly. If a stool retest is negative following completion of the treatment, the subject may be entered into the study. If, after treatment, the subject tests positive for *H. pylori* at the retest, s/he is to be excluded from the study.

11.9. Visit Schedules

The table in Appendix B provides an overview of the schedule of exams and procedures for the study.

11.9.1. Screening Visit (Within 8 Weeks Prior to the Index Procedure)

At the screening visit, the following procedures/assessments will be performed to determine subject eligibility:

- Informed consent prior to the conduct of any study-related procedures
- Demographics (ethnicity, age, gender, education, marital status)
- Medical history, especially the assessment of risk factors and morbidities related to obesity and age when subject first noticed obesity
- Concomitant medications
- Physical examination
- Body mass assessment (body weight, height, calculation of BMI, and measurement of circumferences)
- Patient Health Questionnaire (PHQ-9)
- Behavioral evaluation by registered dietitian, behavioral specialist, or mental health professional
- Urine pregnancy test for females capable of becoming pregnant
- Stool test for *H. pylori*
- Blood tests
 - CBC with differential
 - Chemistry panel 20
 - Fasting lipid panel
 - Fasting blood glucose, insulin, HbA1c, C-reactive protein
- EKG
- Assessment of enrollment eligibility (inclusion/general exclusion criteria)

Each subject will be assessed for suitability to participate in the study by the site Investigator.

Subjects who meet all the inclusion criteria but none of the exclusion criteria will be scheduled for a baseline visit.

11.9.2. Baseline Visit (Within One Week Prior to the Index Procedure)

The following evaluations/procedures are to be performed within 7 days prior to the index procedure:

- Abbreviated physical examination including vital signs (temperature, systolic/diastolic blood pressure, respiration rate, heart rate)
- Body mass assessment (body weight, calculation of BMI, and measurement of circumferences)
- Concomitant medications
- IWQOL-Lite assessment
- Eating Inventory assessment
- Visual Analog Scale assessment
- Urine pregnancy test for females capable of becoming pregnant
- Blood tests
 - CBC with differential
 - Chemistry panel 20
 - Lipid levels and lipoproteins,
 - Glucose, insulin, HbA1c, high sensitivity C-reactive protein
- Assessment for eligibility
- Brief lifestyle counseling according to Appendix C, including recommendation and instruction to follow the caloric target of 1200-1500 kcal/day for subjects ≤ 114 kg (≤ 250 lb) and 1500-1800 kcal/day for subjects > 114 kg (> 250 lb)

If the subject is no longer eligible for the study due to a change in the subject's condition, such as pregnancy, abnormal blood test values, or weight change resulting in a BMI outside of the protocol range, the subject will be excluded from the study and documented as a screen failure.

This visit is not required in subjects whose screening visits and tests are performed within 7 days of the index procedure. In this case, data collected from the screening visit will serve as baseline data.

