6.2. Secondary Effectiveness Endpoints

The following secondary endpoints will be assessed in this study:

- Proportion of subjects who achieve at least 7% and 10% TBL at 12 months in the Treatment versus Control group
- Percent total body weight loss over 12 months in the Treatment versus Control group
- Percent excess weight loss over 12 months in the Treatment versus Control group
- Proportion of subjects who achieve at least one obesity class reduction at 12 months in the Treatment versus Control group
- Change of BMI over 12 months from baseline in the Treatment group
- Change in weight-related quality of life over 12 months as assessed by IWQOL-Lite Questionnaire
- Change in eating behavior over 12 months as assessed by the Eating Inventory
- Change in appetite, hunger and fullness over 12 months as assessed by Visual Analog Scales.
- Change in comorbid conditions over 12 months in the Treatment group:
 - a) Prevalence of the metabolic syndrome and its individual components
 - b) Glucose, insulin, and insulin resistance (as estimated by HOMA)
 - c) High sensitivity C-reactive protein (hsCRP)
 - d) Lipid levels (LDL-C, HDL-C, and triglycerides)
 - e) Blood pressure
 - f) Waist circumference

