Before the subject is discharged, s/he is to be provided with a subject information card. This card provides the phone number and name of the person to contact in case s/he needs medical attention related to the therapy. Additionally, the subject can provide this card to an emergency room doctor, allowing them to contact the Primary Investigator and obtain information about the study. A sample of the card is provided in Appendix G.

The subject should be placed on a liquid diet for 3 days, followed by soft food for a week, slowly returning to normal food in 10 days.

The following procedures/assessments will be performed during this visit:

- Abbreviated physical examination including vital signs (temperature, systolic/diastolic blood pressure, respiration rate, heart rate)
- Body mass assessment (body weight, calculation of BMI, and measurement of circumferences)
- Assessment of medications
- Endoscopic assessment
- Confirmation of eligibility
- TPS placement procedure

- Assessment of AEs that occurred during the procedure

Post-Procedure Follow-Up Visits

Post-procedure follow-up visits are summarized in Appendix B. They include:

- Office visits at 1 week, and 1, 2, 4, 6, 9, 12 months
- Endoscopic assessments at 2, 6, and 12 months
- Visual Analog Scale assessment at 1 week and 1, 6, and 12 month(s)
- Eating Inventory assessment at 1 week and 1, 6 and 12 month(s)
- Blood tests at 6 and 12 months
- IWQOL-Lite at 6 and 12 months
- Device removal at 12 months
- AE assessments at each follow-up visit
- Brief lifestyle counseling at each follow-up visit and brief telephone calls at 7, 8, 10, and 11 months.

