APPENDIX B: SCHEDULE OF EVENTS

Evaluation	Visit	Screen	Baseline	Index Procedure	1wk	1M	2M	4M	6M	7M	8M	9M	10M	11M	12M
	Days	Within 56 days	Within 7 days	Day 0	D7 ±2	D30 ±7	D60 ±14	D120 ±14	D180 ±14	D210 ±7	D240 ±7	D270 ±21	D300 ±7	D330 -14	D365 ±30
Informed consent		X													
Patient demographics		X													
Medical history		X													
Current medication		X	X	X	X	X	X	X	X			X			X
Psychological evaluation		X													
Inclusion criteria		X	X												
Exclusion criteria (general)		X	X												
Exclusion criteria (endoscopic)				X											
Lifestyle counseling			X		X	X	X	X	X			X			X
Follow up telephone call										X	X		X	X	
Height		X													
Weight		X	X	X	X	X	X	X	X			X			X
BMI		X	X	X	X	X	X	X	X			X			X
Body circumference		X	X	X	X	X	X	X	X			X			X
Physical exam		X	X ¹	X ¹	X ¹	X ¹	X ¹	X ¹	X ¹			X ¹			X
EKG		X													
CBC w/differential		X	X												
Chemistry panel 20		X	X												
Blood tests ²		X	X						X						X
Urine pregnancy test		X	X												
Stool H pylori test		X													
Patient Health Questionnaire		X													
IWQOL-Lite			X						X						X
Satiety Assessments (VAS & Eating Inventory)			X		X	X			X						X
Adverse event assessment				X	X	X	X	X	X			X			X
Blinding assessment					X										X
Device removal															X
Study exit															X

1 – Abbreviated physical: temperature, systolic/diastolic blood pressure, respiration rate, heart rate

2 -- Blood tests include lipid panel, fasting blood glucose, insulin, HbA1c, C - reactive protein

3 – For Treatment group only

APPENDIX C: LIFESTYLE MODIFICATIONS PROGRAM...REDACTED

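### When the Baseline visit is waived (11.9.2), no visit list schedules a pre-procedure IWQOL-Lite, Eating Inventory or VAS, although three secondary endpoints are changes from that baseline

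*Combined protocol and SAP*

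**What the plan says.** Protocol section 11.9.2 allows the Baseline visit to be skipped: "This visit is not required in subjects whose screening visits and tests are performed within 7 days of the index procedure". It names the substitute in the next sentence: "In this case, data collected from the screening visit will serve as baseline data".

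The screening list in 11.9.1 opens with "At the screening visit, the following procedures/assessments will be performed to determine subject eligibility". Its only questionnaire is the PHQ-9, alongside a behavioral evaluation. The Day 0 list in 11.9.3 ("The following procedures/assessments will be performed during this visit") has no questionnaire.

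The general sections call for the instruments at baseline. Section 11.5 says of the VAS and the Eating Inventory: "These instruments will be administered at the baseline, 1 week, and 1, 6, 12 month(s) visits". Section 11.7 says that the IWQOL-Lite "will be collected at baseline and at the 6- and 12-month follow-up visits". Neither section refers to the waiver.

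Section 6.2 makes all three instruments secondary endpoints defined as change, for example "Change in weight-related quality of life over 12 months as assessed by IWQOL-Lite Questionnaire". Section 15.5.4 analyses secondary endpoints on observed data and tests, within each group, whether the change from baseline is centred on zero.

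**The concern.** The substitution rule works only if screening collects whatever Baseline would have collected. For weight, BMI, circumferences, medications and the endpoint blood tests it does. For the three questionnaires it does not, so the rule points to a source that lacks the data.

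A pre-treatment questionnaire that is not given cannot be recovered afterwards. The plan has no rule for a missing baseline on these endpoints: the multiple imputation in 15.5.3 is for follow-up weights only. A subject without a baseline score has no change score. That subject leaves every change summary and within-group test for that instrument. The subject also leaves the between-group mixed model if its response is the change score, which 15.5.4 does not state.

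**Working it through.** The plan gives no figure for waiver use, so there is no stated number to reproduce. The check has two parts: a comparison of the visit lists, and a size calculation under an assumed waiver share.

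**Step 1. Visit lists side by side** (11.9.1, 11.9.2, 11.9.3, and the same columns of Appendix B)

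| Item | Screening | Baseline | Day 0 |
|---|---|---|---|
| Weight, BMI, circumferences | yes | yes | yes |
| Lipids, glucose, insulin, HbA1c, CRP | yes | yes | no |
| IWQOL-Lite | no | yes | no |
| Eating Inventory | no | yes | no |
| VAS | no | yes | no |
| Lifestyle counseling with caloric target | no | yes | no |

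The Appendix B row "Satiety Assessments (VAS & Eating Inventory)" is marked at Baseline, 1 week, and 1, 6 and 12 months. The IWQOL-Lite row is marked at Baseline, 6 and 12 months. Section text and schedule agree. Four Baseline items therefore have no other pre-procedure slot: the three questionnaires and the first counseling session.

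**Step 2. What one waiver subject loses.** If the lists are followed, all 3 baseline questionnaires are absent. The first Eating Inventory and VAS come at 1 week and the first IWQOL-Lite at 6 months, all after the procedure. Post-procedure assessments left without a baseline: IWQOL-Lite 2 + Eating Inventory 4 + VAS 4 = 10.

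**Step 3. How many could use the waiver.** Section 9.2.1 requires a PPI for at least one week before the procedure, and consent at screening precedes any study procedure (11.9.1). A subject not already on an equivalent PPI starts it at screening at the earliest, so the procedure is at least 7 days later. The waiver needs at most 7 days. The two meet only if screening falls at about day −7. Other rules narrow the window for some subjects:

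- two weeks off NSAIDs and aspirin other than low dose (9.1.2);
- a negative *H. pylori* stool test (11.8);
- at least a week of glucose readings, then review, for subjects on sulfonylureas, repaglinide or nateglinide (10.3.2.1).

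The share w is therefore probably low. I assume 2% to 10%.

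**Step 4. Size.** Planned N = 270 (15.4). Subjects without a baseline = 270w. At constant standard deviation and with no other dropout, intervals for mean change widen by 1/√(1 − w).

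| w (assumed) | Subjects, 270w | Interval width factor |
|---|---|---|
| 2% | 5.4, about 5 | 1/√0.98 = 1.01 |
| 5% | 13.5, about 14 | 1/√0.95 = 1.03 |
| 10% | 27 | 1/√0.90 = 1.05 |

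**Step 5. Direction.** Randomization takes place on the day of the procedure, after endoscopic screening (5.3), so waiver use is settled before the arm is known. The loss is expected to fall on both arms in the same proportion.

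**The case against.** The strongest reply is that 11.5 and 11.7 call for the instruments at baseline with no exception. The purpose of the waiver is presumably to avoid repeating recent tests, so a sensible site would give the questionnaires at the screening visit that doubles as baseline. This stands in part. A reader might infer that waiver subjects certainly have no baseline. The documents do not support that; they show only that no visit list schedules one. But 11.5 ties the time point to the baseline visit, which is the visit being waived, and neither section says where the instruments then go. One site may add them and another may not.

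A second reply is that few subjects will qualify. The PPI lead-in makes this likely, and it is why the range stops at 10%. A reader might extend the calculation to a quarter or a half of the cohort; nothing in the documents supports shares of that order.

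A third reply is that these endpoints only support the main result. This also stands. Section 15.4 does not size the trial for them, and 15.1 treats their tests as an aid to interpretation that study success does not depend on.

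**Conclusion.** The gap is real and the consequence is small. The waiver in 11.9.2 names screening data as the baseline, and the screening list lacks three instruments whose change from baseline is a secondary endpoint. A site that follows the lists would lose those baselines permanently.

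At an assumed 2% to 10% waiver use, about 5 to 27 of 270 subjects are affected on each of the three endpoints, and intervals are about 1% to 5% wider. This rests on the assumed share, on sites not adding the questionnaires on their own initiative, and on no other missing data.

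A reader might infer bias between arms or damage to the main result. Neither follows. The waiver precedes randomization, and weight is measured at both screening and Day 0, so the co-primary endpoints are untouched. The case for acting rests on an instruction that does not work as written, a measurement that cannot be repeated, and a very cheap remedy.

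**What to change.** Add one sentence to 11.9.2: if the Baseline visit is waived, the IWQOL-Lite, the Eating Inventory and the Visual Analog Scales, together with the baseline lifestyle counseling and its caloric target, are completed at the screening visit that serves as baseline. Add a matching footnote to those rows of Appendix B. The counseling belongs in the sentence because the same waiver removes the only session before the procedure.

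Do not offer Day 0 as an alternative for the VAS. Subjects are then prepared for endoscopy (11.9.3). If that preparation includes fasting, which is my assumption, their hunger and fullness scores would not be comparable with those from an ordinary Baseline visit.

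The cost is a slightly longer screening visit for the few subjects who use the waiver. No visit is added, and eligibility and the primary analysis do not change.

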11.9.3. Index Procedure (Day 0)

The TPS placement procedure will be performed under general or monitored anesthesia care (MAC). Eligible subjects will undergo standard preparation for an endoscopic procedure, followed by an endoscopic assessment of the esophagus, stomach, antrum, pylorus and duodenum. Subjects who meet the endoscopic exclusion criteria will be considered an endoscopic screening failure and excluded from the study.

Subjects who do not possess any endoscopic exclusion criteria will be randomized into Treatment or Control group using a web-based randomization system provided by the study data management organization. Procedure details can be found in the instruction for use (IFU). In brief, a TPSS Access Sheath is inserted over the gastroscope using standard techniques to position the distal tip approximately 6 cm below the gastroesophageal junction. Endoscopic visualization is used to monitor inflation of the distal positioning balloon on the Access Sheath and confirm final insertion position. After removal of the gastroscope and obturator, the TPS Delivery Device is lubricated and inserted into the Access Sheath until fully-seated with the connectors engaged. The TPS Delivery Device is placed on the TPSS Stand and connected to the insufflation system. Deployment of the TPS is accomplished by forward rotation of TPS Advance Torque Knob on the delivery device handle. Following actuation of the TPS locking mechanisms on the TPS Delivery Device, the formed TPS is released into the stomach and the Access Sheath and TPS Delivery Device are withdrawn from the patient. A final endoscopic evaluation is performed to inspect the final device configuration and assess the gastroesophageal tissues prior to completion of the procedure.

In the Control subject, the sham procedure consists of anesthesia and the TPSS Access Sheath placement but no TPS delivery. Effort will be made so that the overall sham procedure time is similar to the TPS placement procedure time.

Subject will be discharged when the site and physician's discharge criteria are met (if designated by the hospital policy and procedures).

Before the subject is discharged, s/he is to be provided with a subject information card. This card provides the phone number and name of the person to contact in case s/he needs medical attention related to the therapy. Additionally, the subject can provide this card to an emergency room doctor, allowing them to contact the Primary Investigator and obtain information about the study. A sample of the card is provided in Appendix G.

The subject should be placed on a liquid diet for 3 days, followed by soft food for a week, slowly returning to normal food in 10 days.

The following procedures/assessments will be performed during this visit:

- Abbreviated physical examination including vital signs (temperature, systolic/diastolic blood pressure, respiration rate, heart rate)
- Body mass assessment (body weight, calculation of BMI, and measurement of circumferences)
- Assessment of medications
- Endoscopic assessment
- Confirmation of eligibility
- TPS placement procedure

- Assessment of AEs that occurred during the procedure

Post-Procedure Follow-Up Visits

Post-procedure follow-up visits are summarized in Appendix B. They include:

- Office visits at 1 week, and 1, 2, 4, 6, 9, 12 months
- Endoscopic assessments at 2, 6, and 12 months
- Visual Analog Scale assessment at 1 week and 1, 6, and 12 month(s)
- Eating Inventory assessment at 1 week and 1, 6 and 12 month(s)
- Blood tests at 6 and 12 months
- IWQOL-Lite at 6 and 12 months
- Device removal at 12 months
- AE assessments at each follow-up visit
- Brief lifestyle counseling at each follow-up visit and brief telephone calls at 7, 8, 10, and 11 months.

11.9.4. One Week Post-Index Procedure (7 ± 2 Days)

The following data are to be collected:

- Abbreviated physical examination (temperature, systolic/diastolic blood pressure, respiration rate, heart rate)
- Body mass assessment (body weight, calculation of BMI, and measurement of circumferences)
- Visual Analog Scale assessment
- Eating Inventory assessment
- Concomitant medications
- Assessment of AEs that occurred since the last visit
- Assessment of blinding
- Brief lifestyle counseling, with specific instruction for participants to transition from a diet of soft foods to a balanced diet of regular foods and calorie target specific to their weight range as described in Section 11.9.2

11.9.5. One Month Post-Index Procedure (30 ± 7 Days)

The following data are to be collected:

- Abbreviated physical examination (temperature, systolic/diastolic blood pressure, respiration rate, heart rate)
- Body mass assessment (body weight, calculation of BMI, and measurement of circumferences)
- Visual Analog Scale assessment
- Eating Inventory assessment
- Concomitant medications
- Assessment of AEs that occurred since the last visit
- Brief lifestyle counseling

